7.3.3 Visit 3.2 (Day 1, for IOP and safety measurements at 16:00 hours)

Inclusion/exclusion criteria will be reviewed again for the qualified individual. Qualified individuals will be examined. Each examination will include:

- Symptomatology: Individuals will be asked "How are you feeling?"
- A non-dilated eye examination will be performed, including IOP measurements and biomicroscopy. IOP must be measured within 30 minutes of the nominal time (i.e., 15:30 to 16:30 hours)

For further evaluation of OAG eyes in the study, at this time, unmedicated (post washout) IOP must be ≥ 15 mmHg and < 35 mmHg in the same eye. For further evaluation of OHT eyes in the study, at this time, unmedicated (post washout) IOP must be ≥ 22 mmHg and < 35 mmHg in the same eye. [REDACTED]

Individuals who do NOT meet this requirement may return for up to 2 additional qualification visits within 1 week of failing the first qualification visit. Individuals returning at an unscheduled visit within 1 week are required to only re-measure IOP in both eyes.

Upon return for an unscheduled qualification visit, such individuals would need to qualify at 08:00, 10:00 and 16:00 hours. Individuals who fail due to IOP being ≥ 35 mmHg in either eye (exclusion criterion) MAY NOT return for additional qualification visits.

As noted in Section 4.2, subjects must qualify in both eyes based upon IOP and ocular history for a subject who qualifies; the study eye will be the eye with the higher IOP at 08:00 hours on Visit 3. If both eyes have the same IOP at 08:00 hours on Visit 3, then the right eye will be the study eye. In each subject, BOTH eyes will be treated.

At this point, eligible subjects will be randomized. The study medication kit containing 2 bottles will be dispensed to the subject, along with dosing and storage instructions by the site staff.

Subjects will be:

- Instructed to administer their masked medication OU at home between 20:00 - 22:00 hours beginning with the first dose on the evening of this study visit
- Instructed to return to the office with their study medication on Week 1 (Day 8)

For post randomization assessments, a window of ± 2 days for Visit 4 is permitted, and a window of ± 3 days for Visits 5 and 6 is permitted.

7.3.4 Visit 4.0 (Week 1 [Day 8], for IOP and safety measurements at 08:00 hours)

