Appendix 2 Procedures

Procedures: Best Corrected Visual Acuity

Best corrected visual acuity (BCVA) is taken at all visits as a measure of ocular function. BCVA will be measured at screening and frequently throughout the study.

Procedure: Distance visual acuity must be assessed using an Early Treatment of Diabetic Retinopathy Study (ETDRS) or equivalent chart. Visual acuity testing should precede intraocular pressure measurement, the administration of topical anesthetic agents, or any examination requiring contact with the anterior segment.

Distance visual acuity will be measured with best correction.

The visual acuity chart may be either retro-illuminated (“back-lit”), or reflectance illuminated. If the latter is chosen, then the illumination must be checked at regular intervals to be consistent with ETDRS guidelines. Standard charts for a distance from subject to chart of 10 feet to 20 feet must be used. Ideally, the subject should be seated. The right eye should be tested first. Sites are directed to refer to the instructions on the commercial ETDRS charts. If there is any question, contact the Sponsor’s monitor.

The subject should attempt to read each letter, line by line, left to right, beginning with line 1 at the top of the chart (20/200 line). The subjects should be told that the chart has letters only, no numbers. If the subject reads a number, he or she should be reminded that the chart contains no numbers, and the examiner should then request a letter in lieu of the number. The subjects should be asked to read slowly, about 1 letter per second, so as to achieve the best identification of each letter. He/she is not to proceed to the next letter until he/she has given a definite response.

A maximum effort should be made to identify each letter on the chart. When the subject says he/she cannot read a letter, he/she should be encouraged to guess. If the subject identified 2 letters (e.g., A or B), he/she should be asked to choose 1 letter and, if necessary, to guess. When it becomes evident that no further meaningful readings can be made despite encouragement to read or guess, the examiner should stop the testing for that eye. However, all letters on the last line should be attempted as letter difficulties vary and the last letter may be the only one read correctly. The number of letters missed or read incorrectly should be noted. Repeat with left eye.

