prior to randomization (Visit 3). Subject symptoms will be queried and blood samples will be taken for clinical chemistry and hematology. All individuals who are qualified for enrollment will have their current ocular hypotensive therapy reviewed to determine the appropriate washout period, prior to Visit 2, as specified in Section 5.7.1 of the protocol.

At Visit 2 (Qualification #1, 08:00 hours), potential study subjects will be questioned with respect to changes in their health (to be recorded as medical history) and concomitant medication use. Study inclusion/exclusion criteria will be reassessed to confirm eligibility. Symptomatology, vital signs, BCVA, IOP, and biomicroscopy assessments will again be performed. The potential subject must have a post-washout IOP ≥ 15 mmHg (OAG) or ≥ 22 mmHg (OHT) and < 35 mmHg in both eyes to qualify for further participation. [REDACTED]

Qualified subjects will return for Visit 3 (Qualification #2, Baseline, Day 1) 2 to 7 days after Visit 2 at 3 time points. Inclusion/exclusion criteria will be reviewed again for the qualified individual at all the 3 time points. At Visit 3.0 (08:00 hours), the subject will be questioned regarding any changes in their health and concomitant medication use. The testing will include recording symptomatology, vital signs, BCVA, IOP, and biomicroscopy assessments. Any symptoms reported at this visit should be entered into medical history. The potential subject must have a post-washout IOP ≥ 15 mmHg (OAG) or ≥ 22 mmHg (OHT) and < 35 mmHg in both eyes to qualify for further participation. [REDACTED]

Qualifying subjects will return for two additional visits on this day (Visit 3.1 at 10:00 hours and Visit 3.2 at 16:00 hours) during which symptomatology, IOP, and biomicroscopy assessments will be performed. The potential subject must have a post-washout IOP ≥ 15 mmHg (OAG) or ≥ 22 mmHg (OHT) and < 35 mmHg in both eyes to qualify for further participation. [REDACTED]

In summary, the following IOP criteria must be met at the qualifying visits in both eyes for the subject to qualify for the study:

Visit, Day, Time	OAG Eyes IOP Requirement (mmHg)	OHT Eyes IOP Requirement (mmHg)
Visit 2, 8:00 hours	≥ 15 & < 35	≥ 22 & < 35
Visit 3.0, Day 1, 8:00 hours	≥ 15 & < 35	≥ 22 & < 35
Visit 3.1, Day 1, 10:00 hours	≥ 15 & < 35	≥ 22 & < 35
Visit 3.2, Day 1, 16:00 hours	≥ 15 & < 35	≥ 22 & < 35

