3. GENERAL ANALYSIS AND REPORTING CONVENTIONS

This section discusses general policies to be employed in the analysis and reporting of the data from the study. Departures from these general policies may be given in the specific detailed sections of this SAP. When this situation occurs, the rules set forth in the specific section take precedence over the general policies.

All continuous study assessments will be summarized by treatment and time point (as applicable) using descriptive statistics (n, mean, median, standard deviation (SD), minimum, and maximum). All categorical study assessments will be summarized by treatment and time point (as applicable) using frequency counts and percentages.

All study data will be listed by treatment, subject, visit, and time point (as applicable). Hypothesis testing, unless otherwise indicated, will be performed at a 2-sided 0.05 significance level. When applicable, two-sided 95% confidence intervals will be reported. All p-values will be displayed to four decimal places, with p-values less than 0.0001 presented as '<0.0001' and p-values greater than 0.9999 presented as '>0.9999'. Differences between each netarsudil group and placebo will be calculated as netarsudil – placebo.

For diurnally adjusted IOP, baseline will refer to the time-relevant measure at Visits 3.0 through 3.2 (e.g. IOP at 08:00 hours at Visit 3.0 will be the baseline for 08:00 hours at Visits 4.0, 5.0, and 6.0, etc.; IOP at 10:00 hours at Visit 3.1 will be the baseline for 10:00 hours at Visits 4.1, 5.1, and 6.1, etc.). For mean diurnal IOP, baseline will refer to the mean diurnal IOP at Visit 3. For all other variables, baseline is defined as the last measurement prior to the first dose of study medication. Change from baseline will be calculated as follow-up visit – baseline visit.

The unit of analysis for efficacy will be the study eye, defined as the eye with the higher IOP at 08:00 hours on Visit 3. If both eyes have the same IOP at 08:00 hours on Visit 3, then the right eye will be the study eye.

All study data will be listed by subject, treatment, and time point (as applicable). In the listings, individual subjects will be identified by a combination of site number and subject number, e.g., XXX-YYY, where XXX is the site number and YYY is the subject number.

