9.6.5 Biomicroscopy

Biomicroscopy results will be listed for both eyes at each visit and time point. A separate listing will be presented for subjects with a criterion change, defined as a +1 unit increase from baseline. Summaries of biomicroscopy results will also be presented for study eyes and fellow eyes by treatment group, visit, and time point in tabular form.

A summary table of the number and percentage of subjects with at least a +1 unit increase in score from baseline will be presented by region, finding, time point and eye (study eye and fellow eye). In addition to each time point, there will be summaries for “At the Final Visit” and “At Any Visit”.

Another summary table will be presented with the number and percentage of subjects who had a finding judged to be clinically significant by region, finding, time point and eye (study eye and fellow eye). Fisher’s exact tests will be used to compare incidence between treatment groups in both tables. Additionally, Conjunctival Hyperemia will be presented using continuous summary statistics for each visit, for the change from baseline to each post-baseline visit. Differences between treatment groups will be tested using two-sample t-tests as well as Wilcoxon rank sum tests.

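### Slit-lamp grades at 08:00 and 10:00 are compared with a pre-dose grade normally taken at 16:00, so one-step changes can be misclassified, although same-hour Visit 3 grades are collected

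*SAP*

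**What the plan says.** SAP section 3 has separate baseline rules. For pressure at a given hour: "For diurnally adjusted IOP, baseline will refer to the time-relevant measure at Visits 3.0 through 3.2". Mean diurnal IOP uses the Visit 3 diurnal mean. Everything else falls under one sentence: "For all other variables, baseline is defined as the last measurement prior to the first dose of study medication". Protocol 9.1 has the same general rule.

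Slit-lamp examination takes place three times before dosing on Day 1. For Visit 3.0 (08:00), SAP 2.2 says: "The testing will include recording symptomatology, vital signs, BCVA, IOP, and biomicroscopy assessments". The later sessions are described as "Visit 3.1 at 10:00 hours and Visit 3.2 at 16:00 hours) during which symptomatology, IOP, and biomicroscopy assessments will be performed". The first dose comes after all three, "beginning with the first dose on the evening of this study visit" (Protocol 7.3.3), between 20:00 and 22:00. Biomicroscopy is repeated at all three hours of Visits 4, 5 and 6.

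SAP 9.6.5 defines no baseline of its own, so the general rule applies. It tabulates subjects with "at least a +1 unit increase in score from baseline will be presented by region, finding, time point and eye", compares those incidences between groups with Fisher's exact test, and lists subjects with a one-step increase. It also summarises change in conjunctival hyperemia as a continuous score by visit.

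Protocol 9.1 adds a second, pre-washout baseline for hyperemia from Visit 1, which SAP 3 and 9.6.5 do not carry over. It would not match hours either, since Protocol 7.1 lets screening occur at any time of day.

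**The concern.** The one-step table is reported by hour, but its reference grade comes from one hour. A post-dose 08:00 or 10:00 grade is normally set against a 16:00 grade, while the matching Day 1 grade goes unused. The plan avoids this mismatch for IOP.

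The hours may not be interchangeable. Each session involves local anesthetic, Goldmann applanation and fluorescein (Protocol 6.16 and Appendix 2). The Visit 3.2 grade follows two such sessions that day. A post-dose 08:00 grade follows none and comes 10 to 12 hours after the evening dose. An upward shift by 16:00 in hyperemia or corneal staining is therefore plausible, although nothing in the documents measures it.

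The criterion is sensitive to small shifts. Moderate hyperemia is an exclusion at Qualification Visit #2, so pre-dose hyperemia is effectively grade 0 or 1, and one step of drift equals the whole criterion. Conjunctival hyperemia is the most frequently reported adverse event with the drug (Protocol 6.9.6). Safety is among the primary objectives in Protocol 2.1 and SAP 2.1 (SAP 9.1 calls it secondary). SAP 13 cuts back efficacy analyses after early closure, but the tested safety tables remain.

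**Working it through.** **Plan figures.** The documents give no expected incidence or power for slit-lamp grades. The sample size in SAP 2.6 concerns IOP only and does not bear on this point.

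**Which grades are compared (scheduled visits)**

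| Post-dose grade | Baseline under SAP 3 | Same-hour grade available |
|---|---|---|
| 08:00 (Visits 4.0, 5.0, 6.0) | 16:00, Visit 3.2 | Visit 3.0 |
| 10:00 (Visits 4.1, 5.1, 6.1) | 16:00, Visit 3.2 | Visit 3.1 |
| 16:00 (Visits 4.2, 5.2, 6.2) | 16:00, Visit 3.2 | Visit 3.2, the same grade |

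Only the first two rows can be affected.

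**How an error arises.** An eye graded 0 at 08:00 and 1 at 16:00 before dosing, then 1 at 08:00 on treatment, is recorded as unchanged although its same-hour change is +1. An eye graded 1 at 08:00 and 0 at 16:00 before dosing, then 1 at 08:00, is recorded as +1 although its same-hour change is nil.

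**Model.** Let p be the same-hour incidence of a one-step increase. Let u and d be the shares of eyes whose 16:00 pre-dose grade is one step above or below the same-hour pre-dose grade. Assume that changes are exactly one step and that this disagreement is independent of later change. Then:

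- recorded incidence = p(1 − u) + (1 − p)d
- recorded arm difference = (p_active − p_placebo)(1 − u − d)

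**Upward drift only (d = 0).** Assume 20% to 30% of eyes are grade 1 at 08:00 pre-dose, and 5% to 20% of the grade-0 eyes read 1 by 16:00.

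- smallest u = 0.70 × 0.05 = 0.035; largest u = 0.80 × 0.20 = 0.16
- p = 30%: 0.30 × 0.965 = 29.0% down to 0.30 × 0.84 = 25.2%
- p = 50%: 0.50 × 0.965 = 48.3% down to 0.50 × 0.84 = 42.0%

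At 10 subjects per arm the loss runs from 10 × (0.30 − 0.2895) = 0.1 to 10 × (0.50 − 0.42) = 0.8 study eyes.

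**Effect on the arm difference.** Assume true incidences of 50% on drug and 15% on placebo, a difference of 35 points. Upward drift alone leaves 35 × 0.965 = 33.8 to 35 × 0.84 = 29.4 points. With disagreement in both directions:

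| u = d | Recorded difference | Exact Fisher power, 10 per arm |
|---|---|---|
| 0 | 35.0 points | 0.20 |
| 0.05 | 35 × 0.90 = 31.5 | 0.15 |
| 0.10 | 35 × 0.80 = 28.0 | 0.11 |
| 0.20 | 35 × 0.60 = 21.0 | 0.06 |

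Power is low in every row. At this sample size the descriptive incidence matters more than the test.

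**Mean hyperemia change.** The arm difference in mean change is the difference in post-dose means minus the difference in baseline means. Baseline grades precede treatment, so the second term has expectation zero whichever pre-dose hour is used. A common drift shifts change within each arm but cancels between arms in expectation.

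**Limit of availability.** After a failed qualification attempt, only IOP has to be measured again (Protocol 7.3.1 to 7.3.3; SAP 2.2). For such a subject the last pre-dose slit-lamp grade may come from another hour or day, and a same-hour grade may not exist.

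**The case against.** The rule is explicit, identical in protocol and SAP, uses only pre-treatment grades and applies to all arms alike. It is a choice rather than a contradiction, and it is not expected to favour an arm. All of that stands.

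No section reports that grades vary between 08:00, 10:00 and 16:00 before dosing. A reader might infer that one-step changes are in fact being misclassified. The documents support only that they can be, and the drift and response rates above are assumptions.

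SAP 9.6.5 also lists and summarises grades at every visit and hour, and tests clinically significant findings by time point. The randomized comparison of 08:00 grades is therefore visible without any baseline. Hyperemia adverse events are judged against screening (Protocol 6.9.2), so their incidence is untouched. This limits the consequence to the one-step tables and listing.

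Two further inferences are tempting and should not be drawn.

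- Hour-specific hyperemia change is not named as the chief tolerability measure. Protocol 6.8 and 9.7.1 list ocular symptoms and adverse events first, and SAP 9.6.5 describes the continuous hyperemia summary by visit.
- The documents do not show that the grading order needs changing. Appendix 2 does protect acuity ("Visual acuity testing should precede intraocular pressure measurement, the administration of topical anesthetic agents") and sets no such order for slit-lamp grades. But the visit descriptions that mention IOP before biomicroscopy are lists, not a stated sequence. Any fixed order would apply before and after dosing alike, and a new procedure would come late in a study already closing early.

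**Conclusion.** The point holds as a modest, inexpensive improvement. The hour mismatch follows directly from SAP 3 and 9.6.5, and in the 08:00 and 10:00 rows it can misclassify one-step changes and dilute the drug-placebo difference in their incidence. Whether it does depends on pre-dose drift that the documents do not measure. Under the assumed drift the understatement is about 1 to 8 percentage points of incidence. With equal disagreement in both directions of up to 20% each, an assumed 35-point difference could fall as low as 21 points. These figures also rest on exact one-step changes and on disagreement independent of response. The practical reach is descriptive safety tables in a study of about 10 subjects per arm.

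**What to change.** In SAP 3 and 9.6.5, define the biomicroscopy baseline for the by-time-point tables and the listing of one-step increases as the same-hour Visit 3 grade: 3.0 for the 08:00 visits, 3.1 for 10:00 and 3.2 for 16:00. Where that grade is missing, for example after requalification, use the last pre-dose grade and flag the subject.

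The any-visit summary would then draw on up to three baselines per eye, so keep the single-baseline version there as a sensitivity table.

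The cost is a few lines of SAP text, a fallback rule, some extra programming and one additional table. No new data and no change to study procedures are needed.

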4. ANALYSIS POPULATIONS

4.1 Randomized Population

The randomized population will include all subjects who were randomized to treatment. Baseline variables and demographic characteristics will be summarized for this population.

4.2 Intent-to-Treat Population (ITT)

The ITT population will include all randomized subjects who have received at least one dose of study medication. This population will be the primary population for efficacy analyses and will be used to summarize all efficacy variables and will summarize subjects as randomized.

4.3 Per-protocol Population (PP)

The PP population is a subset of the ITT population, which will include those subjects who do not have major protocol violations likely to seriously affect the primary outcome of the study as judged by a masked evaluation prior to the unmasking of the study treatment. This population will be the secondary population for efficacy analyses and will be used to summarize a subset of efficacy variables. If the PP and ITT populations are exactly the same, then additional efficacy analyses on the PP population will not be performed. The PP population will summarize subjects as treated.

4.4 Safety Population

The safety population will include all randomized subjects who have received at least one dose of study medication. This population will be used to summarize safety variables and will summarize subjects as treated.

5. STUDY SUBJECTS

5.1 Disposition of Subjects

Subject randomization, analysis populations, study completion, and withdrawal from the study will be summarized and listed for all randomized subjects. The summary table will include the numbers of subjects randomized and included in the analysis populations by randomized treatment group for the ITT population and by actual treatment group for the PP and Safety populations. It will also include the numbers of subjects who completed and discontinued from the study. The reasons for subject discontinuation and test agent discontinuation will be summarized for the applicable subjects. Reasons for subject discontinuation will include adverse event (AE), withdrawal of consent, non-compliance, lost to follow-up, lack of efficacy, disallowed concurrent medication, investigator decision, protocol violation, death, and an “other” category for reasons other than those previously listed.

By-subject listings will include randomization information, actual treatment assigned, first and last dose dates, exposure, study eye, and analysis population inclusion. For subjects who prematurely discontinue following randomization, an additional by-subject listing will be provided that shows treatment assignment, sex, age, date of last visit, date of last dose, treatment duration at time of discontinuation, study day of discontinuation, and reason for discontinuation. Study day of discontinuation will be calculated as (date of discontinuation – date of Visit 3 date + 1). Note that date of first dose is not collected, but will be assumed to be the Visit 3 date. Treatment duration will be calculated as the (Date of Last Dose – Visit 3 Date + 1).

5.2 Protocol Deviations

Protocol deviations will be evaluated for all subjects. Major protocol violations will be judged by a masked evaluation and summarized in writing prior to the unmasking of the study treatment, for the purpose of selecting the PP population. All subjects having a protocol deviation will be identified in a subject data listing. The number of subjects with protocol deviations and level of deviations (major or minor) will be summarized by treatment group and severity of the deviation along with the disposition data.

Failure to meet all Protocol Inclusion Criteria or meeting any Exclusion Criterion will also be considered for categorization of Protocol Deviation. Inclusion and Exclusion Criteria will be presented in a by-subject listing.

6. DEMOGRAPHIC AND OTHER BASELINE CHARACTERISTICS

6.1 Demographics and Baseline Characteristics

Demographic and baseline characteristics will be summarized by treatment group and listed for the randomized population. Demographic parameters will include sex, age in years at signing of informed consent form (ICF), Japanese ethnicity (1st or 2nd generation), prior hypotensive therapy, and time on current hypotensive therapy. Baseline characteristics will include study eye diagnosis of OHT or OAG, length of time since study eye diagnosis of OHT or OAG, study eye IOP at screening, and study eye mean diurnal IOP at baseline. Additionally, means for both the study eye and the fellow eye will be summarized separately for the baseline ocular measurements of deviation in visual fields, central corneal thickness, and cup-to-disc ratio.

Age will be reported in years and calculated in SAS using the formula:

$$\text{Age} = \text{Floor}((\text{ICFDT} - \text{DOB}) / 365.25)$$

where ICFDT is the date the subject signed the informed consent, DOB is the subject's date of birth, and Floor takes the integer part of the result.

Tests of differences between the treatment groups will be performed for both demographic and baseline characteristics. Categorical responses will be tested using Fisher's exact tests. Continuous measures will be tested using an analysis of variance model with treatment as the only explanatory variable.

